#### 3.3. Quantitative Outcomes

Measures will be administered to participants by a trained researcher at baseline (n=446), 12 weeks (n=446), 6 months (primary outcome, n=446), and 12 months post-randomisation (naturalistic follow up, n= approx. 300/participants recruited  $\geq 12$  months before trial end date). All measures and their time-points of completion are presented in Table 1.

 Table 1: Summary of assessments

			TIMELINE				
Assessment	Source	Method of Completion	Screening	Baseline	12 Weeks	6 Months	12 Months *
			PARTICIPANT- YOU	NG PERSON			
Screening	Screening Log	Research Assistant (RA) /Site staff	X				
Mood and Feelings Questionnaire (MFQ-C)	Questionnaire	Self-completion	X	Х	Х	Х	X
Contact Details	CRF	Research Assistant/Participant		X	YTU to be notified of changes to contact details		itact details
Demographics	CRF	Self-completion/RA assistance if requested		X			
Eligibility (including Inclusion and Exclusion Criteria)	CRF	PI/Research Assistant/PIs Delegate at site		Х			
Consent	Paper/Online Consent Form/REDCap	Self-completion / Research Assistant		Х			
Strengths & Difficulties Questionnaire (SDQ)	Questionnaire	Self-completion/RA assistance if requested		X	Х	Х	X
Development and Well- Being Assessment (DAWBA)	Online	RA led alongside participant if requested		X			
Revised Children's Anxiety and Depression Scale (RCADS) Brief Version	Questionnaire	Self-completion/RA assistance if requested		Х	Х	Х	Х

Behavioural Activation for Depression (BADS)	Questionnaire	Self-completion/RA assistance if requested		X	Х	X	X				
Self- harm & suicidality questions	CRF	Self-completion/RA assistance if requested		Х	Х	Х	Х				
Goal based outcomes	CRF	Self-completion/RA assistance if requested		X	X	Х	X				
Child Health Utility -9 Dimensions (CHU-9)	Questionnaire	Self-completion/ RA assistance if requested		Х	Х	Х	X				
EQ-5D-Y	Questionnaire	Self-completion/RA assistance if requested		X		Х					
Healthcare Service Use schedule	CRF	Self-completion (with assistance from carer)		X	X	Х	X				
Aspects of Care Contamination Checklist	CRF	Self-completion/RA assistance if requested			X	Х	X				
Working Alliance Inventory (WAI-S)	Questionnaire	Self-completion	(Collected halfway through intervention delivery)								
End of BA treatment Questionnaire	Questionnaire	Self-completion	(Collected after final session of BA therapy)								
Optional Qualitative Interview	Semi-structured interview	Interview				X					
			PARENT/CA	RER							
Consent	Paper/Online Consent Form/REDCap	Self-completion / Research Assistant		X							
Demographics	CRF	Self-completion/ RA assistance if requested		X							

Strengths & Difficulties	Questionnaire	Self-completion/RA								
Questionnaire (SDQ)-		assistance if requested		X	X	X	X			
Parent version		·								
Development and Well- Being Assessment	Online	RA led alongside		X						
(DAWBA)		participant if requested								
Mood and Feelings		Self-completion/RA								
Questionnaire (MFQ)  Parent version	Questionnaire	assistance if requested		Х	X	X	X			
Carer EQ-5D-5L	Questionnaire	Self-completion/RA assistance if requested		Х		X				
Generalised Anxiety Disorder (GAD-7)	Questionnaire	Self-completion/RA assistance if requested		х		Х				
Patient Health Questionnaire (PHQ-9)	Questionnaire	Self-completion/ RA assistance if requested		х		X				
Optional Qualitative Interview	Semi-structured interview	Interview				Х				
		R	ESEARCH ASSISTANT/I	RESEARCH TEAM						
						(X – IF				
Treatment as Usual	Questionnaire	Self-completion/Clinical				PARTICIPANT IS				
Questionnaire		records				NOT DUE A 12	X			
Questionnane		records				MONTH FOLLOW-				
						UP)				
Safety Reporting	CRF	Research								
		Assistant/PI/Clinician								
BA Completion (Discharge Information)	CRF	Clinician/Research Team			X (collected throughout)					
Trial withdrawals	CRF	Research Assistant/PI/Clinician	X (collected throughout)							

Table 2: Summary of BAY therapist assessments.

Assessment	Source	Method of Completion										
			Pre- trial	1 st session	2 nd session	3 rd Session	4 th Session	5 th Session	6 th Session	7 th Session	8 th Session	End of trial
			delivery	Session	30331011	Session	Session	30331011	30331011	30331011	30331011	triai
BAY THERAPIST												
Demographics	CRF	Therapist	Х									
BA Session Log	Questionnaire	Therapist		X	X	X	X	X	X	X	X	
Safety Reporting	CRF	Therapist	X (collected throughout)									
End of BA treatment Questionnaire	Questionnaire	Therapist									X (after final session)	
Fidelity to BA Checklist*	CRF	Independent Assessor										Х
Qualitative Interview	Semi- structured interview	RA led										х

\* Random selection of recordings based on pre-selection criteria: commence in year 2 of trial

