## 3.3.1 Descriptions of outcome measures & assessments

A mixed methods approach will use quantitative and qualitative methods, and will involve trial participants, parents/carers, therapists delivering the BA intervention component, and researchers involved in recruitment for the trial.

Participants will be requested to complete a questionnaire at baseline, 12 weeks and 6 and 12-months (naturalistic sample) post randomisation. Participants will be required to complete their questionnaires in-person or online with support from a researcher who is blind to the treatment allocation.

The recruitment period ends 6 months prior to the end of the follow-up stage, to allow all primary outcome data (6 months) to be collected. Participants who are recruited with 1 year prior to the end of the follow-up period will be asked to complete a 12 month follow-up assessment (n= approx. 300/participants). Participants recruited any closer to the end of the follow-up stage will be required to complete the 6 month follow-up only. This will provide an indication of the clinical and cost effectiveness of the intervention at 12 months in a sub-set of participants.

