#### Aspects of Care Questionnaire

We developed the Aspects of Care Questionnaire (based on the COMBAT study measure) that has 4 items to help assess contamination, i.e. where an individual randomised to treatment as usual has inadvertently or intentionally received elements of BA. The items are 4 statements that correspond to BA-specific activities: 1. "I talked to my therapist about the things and people that I value in my life." 2. "I made plans for activities I enjoy and necessary tasks/routines in a weekly activity diary." 3. I wrote down things I did for pleasure and necessary tasks/routines in a weekly activity diary." 4. "I gave an ACE score (Achievement, Closeness, Enjoyment) to activities I completed in a weekly activity diary." Responses to each item are: 'yes, 'no' or 'I don't know'. Participants in the intervention group would be expected to answer 'yes' whereas participants randomised to treatment as usual would be expected to answer "no" or 'I don't know'.

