## 5. STUDY SETTINGS

The study will be conducted within CAMHS sites responsible for providing support to young people with moderate and severe depression. These sites will be involved in the identification of study participants and will be the locations for intervention delivery. The site must have a BAY trained therapist (trained by psychology leads based within each Trust, PI and psychologist PI from the study) and local supervisor to deliver the BA component. To allow for the option of remote delivery of BA, the site must also have access to the required software and technology to be able to deliver the BA sessions using

video conferencing software. Each CAMHS site will also provide treatment as usual for each participant, which will include access to any urgent care that may be required.

Research Assistants will be based either within CAMHS or their R&D unit within the NHS Trust, and they will be responsible for recruitment and data collection at all timepoints. Some measures will be collected by the trial managers to avoid unblinding the RAs.

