#### 7.5 Post Randomisation

#### 7.5.1 Blinding

All research assistants collecting follow up data will be blind to participant group allocation. To minimise instances of unblinding, RAs will NOT be informed of, or involved in group allocation, organising therapy sessions, collecting end of treatment questionnaires, completing SAE forms, or access allocation information in the study's database. These duties will be the responsibility of the Trial Managers, with additional support from the qualitative researcher as required, who does not need to be blind to treatment allocation. The RAs will remind each participant at the beginning of their follow-up meetings not to tell the RA about their treatment or who they saw as part of their involvement in the BAY project. Clinical teams will also be trained on the importance of minimising blinding.

If unblinding occurs all blind breaks including accidental unblinding will be recorded by the trial manager and reviewed by the Chief Investigator for patterns in unblindings and be reported to the TSC and DMEC. If unblinding occurs and if feasible an RA from another site will collect follow up data from the young person and carer (if applicable).

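### The Aspects of Care contamination checklist may be completed with help from research assistants who must stay blind, which opens an avoidable route to unblinding from 12 weeks onward

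*Protocol*

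**What the plan says.** Section 3.3 states that "Measures will be administered to participants by a trained researcher". Table 1 in that section lists the "Aspects of Care Contamination Checklist" at 12 weeks, 6 months and 12 months, with completion method "Self-completion/RA assistance if requested". Section 3.3.1 has participants "complete their questionnaires in-person or online with support from a researcher who is blind to the treatment allocation".

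The description of the Aspects of Care Questionnaire in section 3.3.1 gives four statements tied to BA: talking with the therapist about valued things and people, planning activities in a weekly diary, recording them there, and giving them an ACE score. On expected answers it says "Participants in the intervention group would be expected to answer" yes, while the treatment-as-usual arm should say no or that they do not know. Section 8.4 confirms that all young people complete the form at follow-up.

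On masking, section 7.5.1 requires RAs who collect follow-up data to be blind and adds: "The RAs will remind each participant at the beginning of their follow-up meetings not to tell the RA about their treatment". It lists tasks kept from RAs: allocation, arranging therapy sessions, end-of-treatment questionnaires, serious adverse event forms and allocation data in the database. The checklist is not on that list. Section 5 says "Some measures will be collected by the trial managers to avoid unblinding the RAs", without naming the measures.

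**The concern.** The checklist exists to show whether a young person has received elements of BA. An RA who helps with it hears roughly what section 7.5.1 asks the participant not to say. The first administration is at 12 weeks, about 14 weeks before the primary assessment (26 − 12, taking 6 months as 26 weeks). Knowledge gained then can persist to the 6-month visit.

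Participants know which treatment they receive, so the blinding of the people collecting the data is the main masking this trial can claim. At stake are that claim and the neutrality of whatever support RAs give with other measures.

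**Working it through.** No arithmetic applies: the protocol gives no figure for how often help is requested or how often blinding is broken. The check is whether the sections fit together.

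1. **Does the form carry information about the arm?** Yes. Section 3.3.1 sets opposite expected answers by arm. The fourth item uses the ACE score, which Table 4 (section 8.1.1) introduces in the programme's second module.

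2. **Can a blinded RA come to see the answers?** Yes. Table 1 permits RA help on request. Sections 3.3 and 3.3.1 place a researcher alongside the participant when questionnaires are completed, and section 5 makes RAs responsible for data collection at every time point. No section says that RAs may not view this form.

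3. **Does a stated safeguard cover it?**
   - The withheld tasks in section 7.5.1 do not include it.
   - The general statement in section 5 names no measure, while Table 1 specifically offers RA help with this one.
   - Other measures that reveal treatment are handled differently. Table 1 lists the WAI-S and the young person's end-of-treatment questionnaire as self-completion only, and section 3.3.1 has an unblinded team member distribute the latter. Section 7.3 defers the RA's review of clinical records for the treatment-as-usual form to the end of the young person's participation. The checklist has neither protection.

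4. **Would order within the visit be enough?** No. The protocol sets no order, and placing the checklist last at 12 weeks would protect only that visit. The answers must also be kept from the RA.

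5. **Which outcomes are exposed?** At 6 months Table 1 allows RA help with the young person's SDQ, RCADS, BADS, self-harm and suicidality questions and goal-based outcomes, and with the parent MFQ and SDQ. The MFQ-C row says self-completion only, so the primary outcome is reached only through the general support described in section 3.3.1.

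**The case against.** Several points on the other side stand and limit the finding.

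- **Help is conditional.** Self-completion is the default, and support in the session does not mean reading the answers. A reader might infer that the checklist is routinely done with the RA; Table 1 does not say so.
- **The answers are imperfect markers of arm.** A reader might infer that each assisted form reveals the allocation. The first three items can arise in usual care: sections 8.2 and 8.4 accept BA-like elements there and list CBT, staff already trained in BA and online material as sources. BA participants who never start or stop early may answer no. Only the ACE item is clearly specific to the programme.
- **The primary outcome is at one remove.** The MFQ-C is rated by young people who know their allocation, and its Table 1 row gives the RA no role in answering.
- **There is a remedy.** Section 7.5.1 has blind breaks logged, reviewed for patterns and reported to the oversight committees, with an RA from another site taking over follow-up if feasible. Nor does the protocol say that the same RA sees a participant at both visits.

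These points reduce the likely harm but do not reconcile the sections. The remedy acts only after blinding is lost, depends on feasibility, and does not prevent the exposure that Table 1 permits.

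**Conclusion.** The inconsistency is real and worth correcting. Followed as written, the protocol lets staff who must be blind help with, and possibly see, a form designed to separate the arms, starting before the primary endpoint. It is a route to unblinding, not certain unblinding. It matters most for the measures that allow RA help; for the MFQ-C any effect is indirect and probably modest.

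The size of any bias cannot be derived from the protocol. A reader might multiply an assumed share of participants asking for help by an assumed shift in MFQ-C points and compare the product with the five-point minimum important difference. Neither input has any basis in the document. Shifting the BA mean alone would also be incomplete, because a set of negative answers tells the RA something about control participants too.

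The conclusion assumes that no document outside the protocol already withholds the checklist from RAs. If a site procedure does so, Table 1 and section 7.5.1 still need to say it.

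**What to change.** - In Table 1, change the checklist's completion method to self-completion, with any help from the unblinded Trial Managers.
- In section 7.5.1, add the checklist to the tasks withheld from RAs, and state that RAs neither assist with it nor see the responses.
- Collect it after the outcome measures for that time point are complete, by REDCap link with RA access to the responses blocked. Section 7.3 also allows paper, so provide a sealed form returned to the Trial Managers for those cases.

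The cost is small. Trial Managers already handle tasks that would unblind RAs, and contamination monitoring under section 8.4 continues unchanged. The downside is perhaps slightly lower completion of the checklist outside the supported meeting. As this is the participant-reported monitor of contamination, and section 9.1 already assumes 70% retention, the Trial Managers should follow up missing forms.

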## 3.3.1 Descriptions of outcome measures & assessments

A mixed methods approach will use quantitative and qualitative methods, and will involve trial participants, parents/carers, therapists delivering the BA intervention component, and researchers involved in recruitment for the trial.

Participants will be requested to complete a questionnaire at baseline, 12 weeks and 6 and 12-months (naturalistic sample) post randomisation. Participants will be required to complete their questionnaires in-person or online with support from a researcher who is blind to the treatment allocation.

The recruitment period ends 6 months prior to the end of the follow-up stage, to allow all primary outcome data (6 months) to be collected. Participants who are recruited with 1 year prior to the end of the follow-up period will be asked to complete a 12 month follow-up assessment (n= approx. 300/participants). Participants recruited any closer to the end of the follow-up stage will be required to complete the 6 month follow-up only. This will provide an indication of the clinical and cost effectiveness of the intervention at 12 months in a sub-set of participants.

# Mood and Feelings Questionnaire (MFQ)

## - Young people

The Mood and Feelings Questionnaire (MFQ) (Angold et al., 1995; Costello & Angold, 1988) is a screening tool for depression in children and young people aged 6 to 19. The MFQ consists of a series of 33 descriptive phrases regarding how the subject has been feeling or acting recently. Respondents are asked whether descriptions in the questionnaire are 'true', 'sometimes true' or 'not true' for them over the past two weeks. The MFQ is scored by summing together the point values of responses for each item and higher scores on the MFQ suggest more severe depressive symptoms (scoring 27 or higher on the long version may indicate the presence of depression in the respondent). Peer-reviewed studies have found the Mood and Feelings Questionnaire to be a reliable and valid measure of depression in children in both clinical and non-clinical samples (Burleson Daviss et al., 2006; Sund, Larsson and Wichstrom., 2001; Wood et al., 1995).

#### - Parents

The MFQ Parent Report is a 34 item measure (Angold et al., 1987). Parents are asked to report how their child has been feeling or acting in the past two weeks. Respondents are asked whether descriptions in the questionnaire are 'true', 'sometimes true' or 'not true' for their child over the past two weeks.

# **Demographics questionnaires**

# - Young People

On entry to the study, participating young people will be asked to complete a short demographic questionnaire to obtain information about their age, gender, ethnicity, religion, family circumstances (who they live with), school meals, and education or work. Young people will also be asked about their digital use, accessibility to digital devices and internet, privacy around use, and preference for online or in-person therapy.

#### - Carers

On entry to the study, participating parents will be asked to complete a short demographic questionnaire to obtain information about their age, gender, ethnicity, religion, and socioeconomic status.

## - Therapists

All professionals involved in the delivery of BA treatment for the trial will be asked to complete a short demographic questionnaire when they are assigned a young person to work with as part of the trial. This will capture information about their professional role, grade, organisation, years in service, age range, sex and previous experience of BA (if any).

# Development and Well-Being Assessment (DAWBA)

# -Young people and parents/carers

The DAWBA is a package of interviews, questionnaires and rating techniques designed to generate ICD-10 and DSM-IV or DSM-5 psychiatric diagnoses on 2-65 year olds (Goodman et al., 2000). The DAWBA covers the common emotional, behavioural and hyperactivity disorders, without neglecting less but sometimes more severe disorders.

Information is collected from up to three sources:

- An interview with 11-17 year olds themselves (Included in the BAY Trial at baseline)
- An interview with the parents of 11-17 year olds (Included in the BAY Trial at baseline)
- A questionnaire completed by teachers of 11-17 year olds. (Not included in the BAY Trial as educational professionals are not involved in the study)

The interviews and questionnaires involve a mixture of open and closed questions and the parent interview takes around 50 minutes to administer and the youth interview takes around 30 minutes to administer.

Information from the different informants (young people and parents) is drawn together by a computer program that also predicts the likely diagnosis or diagnoses, generating six probability bands, ranging from a probability of less than 0.1% of having the relevant

diagnosis to a probability of over 70% of having the relevant diagnosis. The initial validation study of the DAWBA suggested it had considerable potential as an epidemiological measure and promise as a clinic assessment (Goodman et. al., 2000).

# Strengths & Difficulties Questionnaire (SDQ)

# - Young People

The SDQ measures emotions and behaviours of YP and the SDQ (25 items) + impact scale will be used here (Goodman, 1997). The SDQ is comprised of 5 subscales: 1) Emotional symptoms; 2) Conduct problems; 3) Hyperactivity/inattention; 4) Peer relationships problems; 5) Prosocial behaviour. All items are rated using the options 'Not true', 'Somewhat true', or 'Certainly true'. Some items are reverse scored, and so a higher score on the SDQ indicates greater difficulties within the subscales.

The extended version of the SDQ asks whether the respondent thinks they have a problem, and if so, enquires further about chronicity, distress, social impairment, and burden to others. This provides useful additional information for clinicians and researchers with an interest in psychiatric caseness and the determinants of service use.

#### - Parents

A parent version of the SDQ (25 items) + impact scale will be given to parents/carers and this will be completed from their perspective on behalf of the child. The above principles of the questionnaire remain the same.

# Revised Children's Anxiety and Depression Scale (RCADS) - Brief Version - 25 items

The RCADS brief version is a 25-item questionnaire that assesses children's depression and anxiety; it is a condensed version of the original 47-item (Chorpita et al., 2000) and has been validated as a self-completed outcome measure for 8-to-18-year-olds. Both versions of the RCADS have sub-scales that capture symptoms in 6 domains: one domain relates to depression and five to anxiety problems (generalised anxiety disorder, panic disorder, obsessive compulsive disorder, separation anxiety disorder and social anxiety). All items are rated on a 4-point Likert-scale from 0 to 3, where 0 = Never, 1 = Sometimes, 2 = Often, and 3 = Always. Raw scores are transformed into t-scores by matching the raw score to its corresponding age and gender normed t-scores (available on the measure's website https://www.childfirst.ucla.edu/resources/). Higher t-scores denote greater clinical need. Clinical cut-offs for the t-scores are: 0-64 non-clinical range, 65-69 borderline clinical range, and  $\geq 70$  clinical range.

This scale is routinely used in CAMHS and will provide information about anxiety, a common comorbid problem in YP with depression; it will also allow for direct comparisons with the other current UK BA trial taking place in school populations (COMBAT).

